## 6 STUDY INTERVENTION/INVESTIGATIONAL PRODUCT

### 6.1 Study Product Description

Valganciclovir is marketed for the treatment of CMV retinitis and the prevention of CMV disease in select transplant patients. In adults, valganciclovir is approved for the treatment of CMV retinitis in patients with acquired immunodeficiency syndrome (AIDS), and for the prevention of CMV disease in kidney, heart, and kidney-pancreas high-risk transplant patients. Valganciclovir is approved for the prevention of CMV disease in kidney transplant patients (4 months to 16 years of age) and heart transplant patients (1 month to 16 years of age) at high risk.

#### 6.1.1 Acquisition

Valganciclovir for Oral Solution will be provided for this study by Genentech Inc. Purified water (USP) for preparation of nonparenteral pharmaceutical products will be obtained at the local investigational pharmacy. Upon request by DMID, the study products will be shipped to the following address:

DMID-Clinical Agents Repository Contract (CAR)  
Fisher BioServices  
[name]  
[name]  
[contact]  
[contact]  
Email: [contact]

Study product (valganciclovir) will be shipped to the investigational site upon request and approval by DMID.

#### 6.1.2 Formulation, Packaging, and Labeling

Valganciclovir for oral solution will be supplied as a white to slightly yellow powder for constitution, forming a colorless to brownish yellow tutti-frutti flavored solution in the following strength: 50 mg per mL. It will be packaged in glass bottles containing approximately 100 mL of solution after constitution. The valganciclovir oral solution formulation does not contain lactose anhydrous.

##### 6.1.2.1 Packaging and Labeling

The study drug will be supplied in its original manufacturer's bottle. Each container will also be labeled in compliance with applicable regulatory requirements, including the FDA-required cautionary statement "Caution- New drug -Limited by Federal (or United States) Law to Investigational Use Only."

---

### **6.1.3 Product Storage and Stability**

Valganciclovir will be provided as a powder for oral solution. Dry powder is to be stored at 25°C (77°F); excursions permitted to 15 °C to 30 °C (59 °F to 86 °F). Store reconstituted oral solution at 2° to 8°C (36 °F to 46 °F) for no longer than 49 days. Do not freeze. Shake bottle well before using.

## **6.2 Dosage, Preparation and Administration of Study Intervention/Investigational Product**

### **6.2.1 Dosage**

Valganciclovir should be dosed at 16 mg/kg body weight, unless specific dosage adjustment conditions (e.g., renal function) have been met, administered orally twice daily for 4 months. Specific dosing volumes will be provided for each subject. Dose modifications for neutropenia, thrombocytopenia, and hepatotoxicity are detailed in Section 6.3.

### **6.2.2 Preparation**

Valganciclovir for Oral Solution will be prepared by the site Research Pharmacist for dispensing to the subject. A new bottle will be reconstituted and dispensed monthly during the 4 month treatment period. Instructions for reconstitution will be provided in the protocol-specific Manual of Procedures (MOP).

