### **6.2.3 Administration**

Valganciclovir oral solution has been shown not to adhere to syringes or to nasogastric tubing. Valganciclovir oral solution should be administered into the subject's mouth via an oral dosing syringe. Valganciclovir will be dispensed monthly. Parent/guardians will be provided with specific storage and administration instructions.

Study product administration should be timed with a feeding. If the subject vomits or spits up following the dosing, re-dosing is not allowed.

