## **6.4 Accountability Procedures for the Study Intervention/Investigational Product(s)**

After receipt of the study product, the site principal investigator (PI) is responsible for study product distribution and disposition and has ultimate responsibility for study product accountability. The Site PI will delegate to the site Research Pharmacist the responsibility for study product accountability. The site pharmacist will dispense valganciclovir in its original bottle and distribute it to the PI (or designee) or to the patient's parent or legal guardian. Each pharmacist will be responsible for and maintain logs of receipt, accountability, dispensation, storage conditions, and disposal of study drug. All study product, whether administered or not, must be documented on the appropriate study product accountability record or dispensing log. Parents/guardians will be instructed to return used bottles to the PI each month. At study completion, the sites will be required to return the drug accountability log to the UAB Central Unit upon request, retaining a copy of the drug accountability form in their study files.

Used and unused study product will be retained at the site until monitored and released for disposition as applicable.

- Upon release for disposition, used or partially used study product will be disposed of by the local site pharmacy in accordance with local regulations.
- Upon completion or termination of the study and after the final monitoring visit, final disposition of the unused study product will be determined by DMID and communicated to the UAB central unit by the DMID Clinical Project Manager for the study. Specifically, all

---

unopened study drug either will be returned to the Clinical Agents Repository (CAR) from the local site pharmacy or destroyed at the site in accordance with local regulations following the direction from the UAB Central Unit or its designee.

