### **7.3.9 Study Day 84 ( $\pm$ 3 days)**

- Obtain 0.5 mL of blood for hematology safety labs
  - WBC count with differential
  - Hemoglobin concentration
  - Platelet count
- Obtain 1.0 mL of blood for chemistry safety labs
  - Alanine aminotransferase (ALT)
  - Direct bilirubin
  - Serum creatinine
- Measure growth parameters
  - Length in centimeters
  - Weight in kilograms
  - Head circumference in centimeters
- Review of adverse events and serious adverse events
- Record concomitant medications
- Obtain 0.7 mL of blood for CMV viral load
- Obtain any updated results from etiological investigations for SNHL
- Collect medication diary, and distribute new one
- Adjust dose of study medication for weight change, if needed

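### One bottle of about 100 mL per month does not cover the stated weight-based dose for a 30-day month once an infant weighs more than about 5.2 kg, so the supply, dose and bottle-return wording need reconciling

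*Combined protocol and SAP*

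**What the plan says.** All references are to the combined protocol and SAP.

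- **Bottle (6.1.2).** The solution comes "in the following strength: 50 mg per mL", and "It will be packaged in glass bottles containing approximately 100 mL of solution after constitution".
- **Dose (6.2.1).** "Valganciclovir should be dosed at 16 mg/kg body weight", "administered orally twice daily for 4 months". The same section promises each subject a specific dosing volume.
- **Weight adjustment (7.3.1 to 7.3.9).** Each visit from Day 7 to Day 84 carries the instruction "Adjust dose of study medication for weight change, if needed". The Month 4 visit (7.3.10) does not.
- **Supply (6.2.2, 6.2.3).** "A new bottle will be reconstituted and dispensed monthly during the 4 month treatment period". Section 6.2.3 repeats the interval without a bottle count: "Valganciclovir will be dispensed monthly".
- **Returns (6.4).** "Parents/guardians will be instructed to return used bottles to the PI each month".
- **Shelf life (6.1.3).** Reconstituted solution may be kept for 49 days.
- **Per-protocol set (11.4.1.2).** This is the population assigned to efficacy, and it consists of children who complete the full four months of medication.

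These sections contain no supply calculation and no rule for a second bottle or an early refill. They do not forbid either. Section 6.2.2 refers to the Manual of Procedures only for how to reconstitute.

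**The concern.** The need for drug rises with weight while the stated supply is flat. If the singular in 6.2.2 is taken at face value, some weight exists above which the protocol cannot be followed in all its parts: the dose, the four-month duration and the one-bottle month cannot all be met.

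Three things are at stake.

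- **Exposure.** The primary objective concerns infants treated for four months. A supply rule could shorten that, and would do so by body weight.
- **Analysis set.** An infant whose bottle runs out early may not count as having completed four months, so a pharmacy rule could influence per-protocol membership.
- **Consistency across sites.** A site that follows the text and a site that supplies extra bottles would deliver different exposure under the same protocol.

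**Working it through.** The plan states no supply figure, so there is nothing to reproduce. The check uses the plan's own inputs.

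**Step 1. Daily volume.** 2 × 16 mg/kg ÷ 50 mg/mL = 0.64 mL/kg/day.

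**Step 2. Break-even weight for one bottle.** Weight = 100 ÷ (0.64 × days).

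- 28 days: 100 ÷ 17.92 = 5.58 kg
- 30 days: 100 ÷ 19.20 = 5.21 kg
- 31 days: 100 ÷ 19.84 = 5.04 kg

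The bottle volume is approximate. With 95 to 105 mL, the 30-day threshold is 4.95 to 5.47 kg.

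**Step 3. Need by weight over 30 days.** Volume = 0.64 × weight × 30.

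- 5 kg: 96.0 mL (a bottle lasts 31.2 days)
- 6 kg: 115.2 mL (26.0 days)
- 7 kg: 134.4 mL (22.3 days)

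Steps 1 to 3 rest on the documents alone.

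**Step 4. Who reaches the threshold?** The documents give an entry minimum of 1775 g and an age of at most 30 days at the start, but no weights during treatment. I therefore *assume* entry weights of 1.775 to 4.5 kg and gains of 15 to 35 g/day, four 30-day months, one 100 mL bottle per month, no carry-over, and a dose that changes only at the listed visits. The whole fourth month is then dosed on the Day 84 weight, which is entry weight + 83 × daily gain.

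The gain that puts the Day 84 weight at 5.21 kg is (5.21 − entry weight) ÷ 83. That is about 33 g/day from 2.5 kg, 27 from 3.0 kg, 21 from 3.5 kg, 15 from 4.0 kg and 9 from 4.5 kg. An infant entering at 1.775 kg does not reach it at any gain assumed.

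For the last bottle, days short = days to cover − 100 ÷ (0.64 × Day 84 weight). The 36-day columns show the variant in which the last bottle is dispensed at Day 84 and must last to about Day 120. The break-even weight is then 100 ÷ (0.64 × 36) = 4.34 kg.

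| Entry kg, gain g/day (assumed) | Day 84 kg | Need, 30 days (mL) | Days short | Need, 36 days (mL) | Days short |
|---|---|---|---|---|---|
| 1.775, 35 | 4.680 | 89.9 | 0 | 107.8 | 2.6 |
| 2.5, 20 | 4.160 | 79.9 | 0 | 95.8 | 0 |
| 3.0, 15 | 4.245 | 81.5 | 0 | 97.8 | 0 |
| 3.0, 30 | 5.490 | 105.4 | 1.5 | 126.5 | 7.5 |
| 3.5, 20 | 5.160 | 99.1 | 0 | 118.9 | 5.7 |
| 3.5, 25 | 5.575 | 107.0 | 2.0 | 128.4 | 8.0 |
| 3.5, 35 | 6.405 | 123.0 | 5.6 | 147.6 | 11.6 |
| 4.0, 25 | 6.075 | 116.6 | 4.3 | 140.0 | 10.3 |
| 4.5, 35 | 7.405 | 142.2 | 8.9 | 170.6 | 14.9 |

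For larger infants a bottle can also fall short earlier. At 4.0 kg and 25 g/day the third month needs 109.5 mL. At 4.5 kg and 35 g/day the second month already needs 113.2 mL.

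**Step 5. Does carry-over rescue it?** Four bottles hold 400 mL. At 3.5 kg and 25 g/day the four months need 72.9 + 86.3 + 99.9 + 107.0 = 366 mL, so leftovers could close the gap if they were kept and were still within 49 days. At 4.0 kg and 25 g/day the total is 82.5 + 95.9 + 109.5 + 116.6 = 404.5 mL, which exceeds four bottles even with full carry-over.

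**The case against.** The strongest reply is that Section 6.2.2 describes a cycle of fresh reconstitution, not a cap of one bottle. Nothing forbids a second bottle or an earlier refill, each infant's dosing volume is known to the site, and a pharmacist who sees that 100 mL will not last would supply more. The daily diary (6.5) and the dispensing logs (6.4) would also show missed days. This is a fair reading of what sites would probably do. It does not remove the conflict, because the text names one bottle and gives no rule for more, so sites are left to choose.

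Several stronger conclusions are tempting, but the documents do not support them.

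- *That most infants would run out before Month 4.* No weight distribution is given. On the assumed grid with 30-day months, an infant entering at 3.0 kg has no shortfall at 15 to 25 g/day, and one entering at 3.5 kg has none at 15 to 20 g/day. Several of the shortfalls that do appear are a day or two.
- *That the last bottle must last 36 days.* No visit is scheduled between Day 84 and Month 4, but dispensing is described only as monthly and is not tied to a visit. Section 6.4 also lets the pharmacist give drug directly to the parent. The 36-day columns are a variant, not the plan.
- *That leftovers are always lost.* Section 6.4 speaks of returning used bottles each month, which may mean emptied ones, and solution keeps for 49 days. The absence of carry-over is an inference.
- *That Month 4 viral load is defined as an on-treatment sample and would be invalidated.* The on-therapy label for Month 4 in Section 3.2.3 belongs to the resistance endpoint. The viral-load endpoint is change through Month 6.

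**Conclusion.** The inconsistency is real and follows from the plan's own figures. One bottle of about 100 mL covers a 30-day month only up to about 5.2 kg (about 5.0 to 5.6 kg for 31 to 28 days), whereas the dose follows weight through Day 84. Taken literally, infants above that weight cannot receive the stated dose for the full four months.

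How many infants this concerns cannot be derived from the documents. On the assumed weights, with 30-day months and no carry-over, the last-month shortfall runs from none to about 9 days. If the last bottle is dispensed at Day 84 and must reach Month 4, it runs from none to about 15 days. Both ranges shrink if leftovers are used.

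The possible consequences are shortened exposure in heavier infants and an effect on per-protocol membership. The definition of the primary endpoint and its confidence bound are not affected. This should be fixed, but it falls short of a must-fix, because the harm arises only where a site applies the one-bottle wording strictly and does not refill.

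**What to change.** The sponsor should reconcile the quantity dispensed in 6.2.2 and 6.2.3, and the bottle-return wording in 6.4, with the bottle volume in 6.1.2 and the weight-based dose and duration in 6.2.1. The supply the protocol states should cover the volume the protocol itself prescribes, and the text should make clear whether leftover solution may be used. No dose, treatment duration or clinical rule is proposed here.

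The cost is about one sentence in 6.2.2 or 6.2.3, a clarification in 6.4, and a matching line in the pharmacy instructions. If the sponsor resolves the conflict by allowing more than one bottle a month, the extra drug is modest. On the assumed grid with 30-day months, the first month needs at most 94 mL and no month more than 142 mL. That means at most one extra bottle in each of the last three months, and none for many infants.

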### **6.2.3 Administration**

Valganciclovir oral solution has been shown not to adhere to syringes or to nasogastric tubing. Valganciclovir oral solution should be administered into the subject's mouth via an oral dosing syringe. Valganciclovir will be dispensed monthly. Parent/guardians will be provided with specific storage and administration instructions.

Study product administration should be timed with a feeding. If the subject vomits or spits up following the dosing, re-dosing is not allowed.

## **6.3 Modification or Termination of Study Intervention/Investigational Product for a Participant**

Bone marrow suppression secondary to CMV can mimic valganciclovir toxicity. Nevertheless, the dosage of valganciclovir will be reduced or terminated if any of the following occur:

### **6.3.1 Neutropenia**

If the ANC reproducibly (within one week) decreases to  $< 500$  cells/mm^3, valganciclovir will be held until the ANC recovers to  $\geq 750$  cells/mm^3, and then administration of drug will resume at the normal dose. If the ANC again reproducibly (within one week) decreases to  $< 750$  cells/mm^3, the valganciclovir dosage will be reduced by 50% and maintained there as long as the ANC remains  $\geq 500$  cells/mm^3. If the ANC reproducibly (within one week) decreases to  $< 500$

---

cells/mm^3 on the 50% dosage, then the study medication will be discontinued. Administration of granulocyte colony stimulating factor (GCSF) is allowed. All administered GCSF doses will be recorded on the concomitant medication sheet. The decision to utilize GCSF is left to the medical discretion of the participating investigator. The parameters for dose adjustment stated above, based upon ANC, will remain in effect even if the patient is receiving GCSF.

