### **6.3.2 Thrombocytopenia**

If the platelet count at baseline was  $\geq 100,000/\text{mm}^3$ , then valganciclovir may be held if the platelet count reproducibly (within one week) decreases to  $< 50,000/\text{mm}^3$ . After the platelet count increases to  $\geq 50,000/\text{mm}^3$ , valganciclovir administration at the normal dose may resume. If the platelet count at baseline was  $< 100,000/\text{mm}^3$ , then valganciclovir may be held if the platelet count reproducibly (within one week) decreases by 50% from baseline value. After the platelet count increases above 50% from baseline value, valganciclovir administration at the normal dose may resume. Recurrence of platelet count below these thresholds will lead to study drug discontinuation.

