### **9.5.2 Discontinuation of Study Enrollment, and Study Treatment For All Subjects, Pending Sponsor Review**

Enrollment and study product administration will be halted for Safety Monitoring Committee (SMC) review/recommendation if any of the following is reported:

- Two or more subjects experience a study product-related SAE.
- 10% or more subjects (with a minimum of 3 subjects) experience the same severe (Grade 3 or higher) study product-related unsolicited AE.
- 20% or more subjects (with a minimum of 3 subjects) experience the same severe (Grade 3 or higher) study product-related non-neutropenia safety laboratory AE.
- 30% or more subjects (with a minimum of 3 subjects) experience severe (Grade 3 or higher) study product-related neutropenia safety laboratory AE.
- 10% or more subjects (with a minimum of 3 subjects) permanently discontinue study treatment according to the criteria outlined in Section 6.3.

Additionally, DMID and the Central Unit may interrupt study dosing and/or study entry at any time if medically indicated. To minimize risk, the medical monitor and the SMC will review cumulative safety data. If enrollment is halted based upon the study halting criteria above or the review of the safety data, upon completion of the review and receipt of advice of the SMC, DMID and the Central Unit Administration will determine if study entry or study dosing may continue according to the protocol.

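### Section 6.3.1 gives no single workable action when, after one hold and return to full dose, the ANC again falls directly below 500

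*Combined protocol and SAP*

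**What the plan says.** Section 6.3.1 of the combined protocol and SAP is prose, with three operative sentences. Each fall must be confirmed within one week.

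1. **Hold.** At a confirmed ANC below 500 cells/mm³, "valganciclovir will be held until the ANC recovers to" at least 750, "and then administration of drug will resume at the normal dose".
2. **Reduction.** The next sentence begins "If the ANC again reproducibly (within one week) decreases to" and gives the trigger as below 750, with no lower limit. The action is that "the valganciclovir dosage will be reduced by 50% and maintained there as long as the ANC remains" at or above 500.
3. **Discontinuation.** If the ANC is confirmed below 500 "on the 50% dosage, then the study medication will be discontinued".

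The same section keeps these rules in force for infants receiving GCSF. Section 9.5.1 refers back to Section 6.3 for individual discontinuation. One of the study-wide halting criteria in Section 9.5.2 counts subjects who "permanently discontinue study treatment according to the criteria outlined in Section 6.3": 10% or more, with a minimum of 3.

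**The concern.** Section 2.3.1 names neutropenia as the drug's primary clinical toxicity. A second fall below the threshold that caused the first hold is therefore a foreseeable event, and a dose-modification rule should give one answer for it. If it does not, one site may hold and return to full dose, another may move straight to half dose, and a third may stop on its own judgement.

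The first stake is safety, because an infant below 500 could be kept on drug or taken off it depending on the site. The second is interpretation. Drug exposure would differ by site. So could membership of the per-protocol efficacy set, which Section 11.4.1.2 restricts to children completing four months of drug. If some sites stop, the secondary outcome on adverse events leading to permanent discontinuation (Section 3.2.2) and possibly the Section 9.5.2 count would be affected as well.

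**Working it through.** The plan gives no figure to reproduce here. The check is to apply the three sentences literally to each stage and each confirmed ANC range, and then to size the affected group.

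**Which sentence applies**

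| Stage | ANC ≥750 | ANC 500–749 | ANC <500 |
|---|---|---|---|
| Full dose, before any hold | no action | no action | hold (sentence 1) |
| Full dose, after a hold | no action | reduce by 50% (sentence 2) | see below |
| 50% dose | stay on 50% | stay on 50% | discontinue (sentence 3) |

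The open cell is full dose after a hold, ANC below 500. Two readings are possible.

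- **Reading A: sentence 1 covers any fall below 500.** Sentence 1 says hold until 750 or above, then the normal dose. Sentence 2 is also triggered, because any value below 500 is below 750, and it says reduce by 50%. The two actions differ. (On the 50% dose, sentence 1 would also be met literally below 500, but there sentence 3 is the specific rule and settles the matter.)
- **Reading B: *again* limits sentence 1 to the first episode.** Only sentence 2 applies. It allows the half dose to continue only while the ANC is at least 500, and that condition is unmet from the outset. Sentence 3 does not apply, because the infant was not on the half dose when the fall occurred. Nothing says whether half dosing starts at once or waits for recovery.

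**Neighbouring rules.** For platelets, Section 6.3.2 states: "Recurrence of platelet count below these thresholds will lead to study drug discontinuation". For ALT, Section 6.3.3 likewise gives discontinuation for a repeat rise to at least 5 times baseline. Each covers a recurrence at its own first threshold explicitly; Section 6.3.1 does not.

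**Size.** Inputs:

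- Expected enrolment is 229 − 11 = 218 (Section 11.2).
- In the earlier six-week versus six-month oral valganciclovir study, 3 participants had drug suspended for ANC below 500. All suspensions fell within the first six weeks, when all 109 were on open-label drug (Section 2.1).
- The fraction of held infants who recur below 500 is not in the documents. I assume 10% to 30%.

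Calculations:

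- Expected first holds: 3/109 × 218 = 6.0. The exact 95% interval for 3/109 scales to about 1 to 17 infants.
- Expected recurrences below 500: 0.10 × 6 = 0.6 to 0.30 × 6 = 1.8, so about 1 to 2 infants. Combining the ends of both ranges gives 0.10 × 1 = 0.1 to 0.30 × 17 = 5.1.

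**Halting rule.** Three discontinuations reach 10% only while there are 3/0.10 = 30 subjects or fewer. At 218 subjects, 0.10 × 218 = 21.8, so 22 are needed.

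**The case against.** The best defence is that *again* makes the rule sequential: first episode, hold and resume; any recurrence below 750, halve; below 500 on half dose, stop. The 500 condition in the second sentence would then govern only how long the half dose lasts, and the third sentence would give the consequence of failing it. On that view there is no contradiction. This has force, and it is why the defect should not be described as a plain conflict. It still leaves the moment of reduction undefined for an infant already below 500.

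Safeguards also limit the harm. Hematology is weekly for the first six weeks (Section 8.2.1.1), any ANC below 500 is notified within 24 hours (Section 9.3.3), and investigators may withdraw therapy for safety (Section 5.3.3.2). None of these says which dose step applies.

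Stronger readings are tempting, but the documents do not support them.

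- **A recurrence is handled less strictly than a first episode.** This needs Reading B, whereas a direct conflict needs Reading A, so the two claims cannot be combined. Even on Reading B it is true only of the immediate action, since no hold is stated. Otherwise recurrence is treated more strictly: a higher trigger, a lasting reduction, and discontinuation as the next step.
- **The 750 trigger after a hold is an inconsistency.** A confirmed 700 needs no action before a hold and a reduction after it. That is a stepped rule with one action in each case.
- **Four to twelve infants are affected.** This comes from the 19% with Grade 3 or 4 neutropenia: 0.19 × 218 = 41, and 10% to 30% of 41 is 4 to 12. Grade 3 in Appendix A extends to 599 after the first week of life, above the hold trigger, and the documents give the direct count of 3 suspensions.
- **Three discontinuations halt the trial.** That is so only with 30 or fewer subjects, and no sentence in Section 6.3.1 orders discontinuation in this case.

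**Conclusion.** The point holds as a gap in a safety rule. For a confirmed fall below 500 on full dose after one hold, Section 6.3.1 gives either two differing actions or one action whose own condition has already failed. I found nothing elsewhere in the document that resolves it.

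The expected number is small, about 1 to 2 infants of 218. That rests on two assumptions: that the suspension rate in symptomatic infants in the earlier study carries over to this asymptomatic population, and that 10% to 30% of held infants recur below 500. So few infants would have little effect on the efficacy estimate and would rarely decide the halting rule. The reason to act is that the instruction fails in a foreseeable case of the drug's main toxicity and costs little to repair.

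**What to change.** The sponsor's medical team should reconcile the three sentences of Section 6.3.1 so that each ANC range (below 500, 500–749, 750 and above) at each stage (full dose before any hold, full dose after a hold, 50% dose) has exactly one action. A small grid would do this. It should state explicitly what applies when a recurrence on full dose goes directly below 500. Which action is right is for the sponsor, and none is proposed here.

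The cost is one clarifying paragraph in the protocol, with no new tests.
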